**Serous Retinopathy and Retinal Vein Occlusion:** Serous retinopathy (fluid accumulation within the layers of the retina) has been observed in patients treated with MEK inhibitors, including cobimetinib. In the randomized phase 3 trial of cobimetinib-vemurafenib *vs.* vemurafenib-placebo, ophthalmologic examinations including retinal evaluation were performed pretreatment and at regular intervals during treatment.

Symptomatic and asymptomatic serous retinopathy was identified in 26% of patients receiving cobimetinib and vemurafenib. The majority of these events were reported as chorioretinopathy (13%) or retinal detachment (12%). The time to first onset of serous retinopathy events ranged between 2 days to 9 months. The reported duration of serous retinopathy ranged from 1 day to 15 months. One patient in each arm developed retinal vein occlusion. Perform an ophthalmological evaluation at regular intervals and any time a patient reports new or worsening visual disturbances.

**CPK elevation and rhabdomyolysis:** Elevations in creatine phosphokinase (CPK) have been observed in patients treated with cobimetinib monotherapy. The majority of CPK elevations reported were asymptomatic, non-serious, and resolved with or without study drug interruption. In Study GO28141 (cobimetinib-vemurafenib *vs.* vemurafenib), elevated CPK was more frequent in the combination arm, (32.4% *vs.* 8.1% all grades, 11.3% *vs.* 0  $>$  G3). CPK increase of more than 10 times the baseline value with a concurrent increase in serum creatinine  $>1.5$  times of baseline occurred in 3.6% of patients receiving combination and in 0.4% of patients receiving vemurafenib. The median time to first occurrence of Grade 3 or 4 CPK elevations was 16 days (range: 12 days to 11 months); the median time to complete resolution was 15 days (range: 9 days to 11 months).

One event of rhabdomyolysis was reported in the Phase 3 study GO28141 (cobimetinib plus vemurafenib), and rhabdomyolysis has been reported in postmarketing experience.

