| Creatine Kinase (CPK) Elevation | General Guidance  | 
Rule out cardiac cause (check ECG, serum cardiac troponin, and CPK-isoforms M and B fraction) and rule out rhabdomyolysis (clinical examination; serum creatinine, potassium, calcium, phosphorus, uric acid, and albumin; and urine myoglobin).
 
Permanently discontinue atezolizumab & CDX-1127 (varlilumab) if there is evidence of clinically significant cardiac injury or rhabdomyolysis.. Assess patient for any history of strenuous physical activity, blunt trauma, or recent IM injections.
 | 
Rule out cardiac cause (check ECG, serum cardiac troponin, and CPK-isoforms M and B fraction) and rule out rhabdomyolysis (clinical examination; serum creatinine, potassium, calcium, phosphorus, uric acid, and albumin; and urine myoglobin).
 
Permanently discontinue atezolizumab & CDX-1127 (varlilumab) and cobimetinib if there is evidence of clinically significant cardiac injury or rhabdomyolysis.
 
Assess patient for any history of strenuous physical activity, blunt trauma, or recent IM injections.
 |
|                                 | Grade 3 that are asymptomatic and deemed not clinically significant | 
Hold atezolizumab & CDX-1127 (varlilumab) pending workup to rule out immune related cardiomyopathy, myocarditis or other cardiac conditions.
 
Workup should generally include ECG, serum cardiac troponin, and CPK-isoforms M and B fraction.
 
Atezolizumab & CDX-
   | 
Hold atezolizumab & CDX-1127 (varlilumab) and cobimetinib pending workup to rule out immune related cardiomyopathy, myocarditis or other cardiac conditions.
 
Workup should generally include ECG, serum cardiac troponin, and CPK-isoforms M and B fraction.
  |

|  |   |  |  |
|--|---|--|--|
|  |   | 
1127 (varlilumab) at fixed dosage only if cardiac etiology is ruled out.
 
Recheck CPK at least once a week. If CPK remains Grade 3 or decreases, continue Atezolizumab & CDX-1127 (varlilumab) at fixed dosage.
   | 
Atezolizumab & CDX-1127 (varlilumab) and cobimetinib may be restarted at previous dose and schedule only if cardiac etiology is ruled out.
 
Recheck CPK at least once a week. If CPK remains Grade 3 or decreases, continue Atezolizumab & CDX-1127 (varlilumab) and cobimetinib at fixed dosage and cobimetinib at current dose and schedule.
  |

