|  | 
Grade 4 CPK elevations or any grade CPK with clinically significant effect (signs of cardiac injury and/or renal injury)
 | 
Hold atezolizumab & CDX-1127 (varlilumab). Work up and treat per institutional guidelines. Rule out immune-related cardiomyopathy, myocarditis, other cardiac conditions, and myoglobin-induced kidney injury.
 
Recheck CPK within 3 days. When CPK is Grade <math>\leq</math> 3 and cardiac immune-related cardiomyopathy has been ruled out, atezolizumab & CDX-1127 (varlilumab) may be resumed
 
Permanently discontinue atezolizumab & CDX-1127 (varlilumab) if Grade 4 CPK elevation recurs or if there is evidence of cardiac/renal
 | 
Hold atezolizumab & CDX-1127 (varlilumab) and cobimetinib. Work up and treat per institutional guidelines. Rule out immune-related cardiomyopathy, myocarditis, other cardiac conditions, and myoglobin-induced kidney injury.
 
Recheck CPK within 3 days. When CPK is Grade <math>\leq</math> 3 and cardiac immune-related cardiomyopathy has been ruled out, atezolizumab & CDX-1127 (varlilumab) and cobimetinib may be resumed with a dose reduction of cobimetinib by 1 dose level on the same schedule (e.g., 60 to 40 mg).
 
If Grade 4 CPK
 |

|   |         |  |  |
|---|---------|--|--|
|   |         | 
injury with any instance of CPK elevation*.
 
*If non-immune related etiology is most likely, resumption of atezolizumab & CDX-1127 (varlilumab) at fixed dose will require consultation with and approval by study PI
 | 
elevation recurs after 1 dose reduction, cobimetinib may be reduced by another dose level (e.g., 40 to 20 mg).
 
Permanently discontinue atezolizumab & CDX-1127 (varlilumab) and cobimetinib if Grade 4 CPK elevation recurs after 2 dose reductions of cobimetinib OR if there is evidence of cardiac/renal injury associated with any instance CPK elevation.
 
*If non-immune related etiology is most likely, resumption of atezolizumab & CDX-1127 (varlilumab) at fixed dose without cobimetinib will require consultation with and approval by study PI
 |

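### The CPK row in Section 7.3 permits re-dosing and orders a permanent stop for the same patient with raised CPK and renal injury, and does not say which prevails

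*Combined protocol and SAP*

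**What the plan says.** All references are to the combined protocol and SAP. The Creatine Kinase (CPK) Elevation part of the Section 7.3 table has a General Guidance row, a row for asymptomatic Grade 3 events judged not clinically significant, and the row at issue.

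- **Entry to the row at issue:** Grade 4 CPK, or "any grade CPK with clinically significant effect (signs of cardiac injury and/or renal injury").
- **Hold and work-up (both columns):** study treatment is held. The conditions to be ruled out include immune-related cardiomyopathy, myocarditis, "other cardiac conditions, and myoglobin-induced kidney injury".
- **Resume sentence (both columns):** it opens "Recheck CPK within 3 days. When CPK is Grade" and sets the threshold at Grade 3 or lower. The only other condition is that "cardiac immune-related cardiomyopathy has been ruled out". The verb is permissive (may). The doublet column lets both antibodies restart; the Arm A column lets all three agents restart, with cobimetinib one dose level lower.
- **Permanent-stop sentence (both columns):** apart from a rule on recurrent Grade 4 elevation, the Arm A column orders permanent discontinuation of all three agents "if there is evidence of cardiac/renal injury associated with any instance CPK elevation". The doublet column has the equivalent for the two antibodies.
- **Starred note (both columns):** if a non-immune cause is most likely, resuming the antibodies needs consultation with and approval by the study PI. In Arm A this is without cobimetinib. The doublet stop sentence carries the asterisk; the Arm A stop sentence does not.
- **General Guidance row:** orders a permanent stop "if there is evidence of clinically significant cardiac injury or rhabdomyolysis". Renal injury is not named as such.

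**The concern.** The row admits patients because they show signs of renal injury, then applies a resume test that does not look at the kidney. A later sentence in the same cell makes renal injury with any CPK elevation a reason to stop for good. Nothing in the row ranks the two sentences. CPK elevation is a recognised cobimetinib toxicity, and Section 2.3.4 describes this as the first human study of the triplet. Investigators at different sites could restart all agents, restart only the antibodies, or stop everything for the same event, and each could point to a sentence in the row. What is at stake is patient safety and uniform conduct across sites.

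**Working it through.** The protocol states no figure here to reproduce, so the check is of the row's decision logic, followed by a rough estimate of how often it might matter.

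**1. Test patient.** Renal injury present, immune-related cardiomyopathy excluded, CPK of Grade 1, 2, 3 or 4. Renal injury is used because General Guidance already names cardiac injury as a stop trigger.

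**2. Does the patient belong in this row?** Yes at every grade: Grade 4 through the first limb, Grades 1 to 3 through the any-grade limb. The neighbouring Grade 3 row is limited to events that are asymptomatic and not clinically significant, so it does not take the patient.

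**3. Apply the two sentences.**

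| CPK at onset | CPK part of resume test | Cardiomyopathy part | Resume permitted? | Permanent stop ordered? |
|---|---|---|---|---|
| Grade 1, 2 or 3 | met at onset | met after work-up | yes | yes |
| Grade 4 | met once CPK falls to Grade 3 or lower | met after work-up | yes, from then | yes |

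The result is the same in both columns. For Grades 1 to 3 the CPK threshold does no work. The only remaining gate is the cardiac one, although the work-up also names kidney injury.

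**4. Add the starred note.** In Arm A there are then three possible outcomes: three agents back with cobimetinib reduced and no PI approval mentioned (resume sentence); no agents (stop sentence); antibodies only, with PI approval (note). With no asterisk on the Arm A stop sentence, the reader must guess what the note qualifies.

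**5. Look for a tie-breaker elsewhere.**
- *General Guidance* stops treatment for clinically significant cardiac injury or rhabdomyolysis. A myoglobin-related kidney injury with raised CPK may well count as rhabdomyolysis, which would point to a stop. Renal injury short of that is not covered.
- *Renal Dysfunction rows* (increased creatinine/CrCl) start at Grade 2. They tie resumption to resolution to Grade 0 or 1, require PI consultation after Grade 3 and bar resumption after Grade 4. These conditions differ from both the resume and the stop sentence of the CPK row, and no row covers a Grade 1 renal event.
- *Section 7.2.2* says that when the responsible drug class is unclear all three agents are held or discontinued, but refers back to Section 7.3 for resumption.

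None of these states which sentence of the CPK row governs.

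**6. Rough frequency.** Inputs: in the randomized phase 3 trial of cobimetinib plus vemurafenib (Section 2.2.2.2.3), CPK above 10 times baseline with creatinine above 1.5 times baseline "occurred in 3.6% of patients receiving combination"; Section 9.2 plans 32 patients per arm, 18 of them in stage 1.

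- Expected cases in a full Arm A: 32 × 0.036 = 1.15.
- Chance of at least one: 1 − 0.964^32 = 0.69.
- At half the rate: 1 − 0.982^32 = 0.44. At twice the rate: 1 − 0.928^32 = 0.91.
- If Arm A stops after stage 1: 18 × 0.036 = 0.65 expected, and 1 − 0.964^18 = 0.48.

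**The case against.** The best defence is that the row can be read in sequence. Signs of injury lead to a hold and a work-up; if the work-up yields evidence of injury, stop; if not, treatment may be resumed. On this reading a permission gives way to a specific order in the same cell, and the starred note is a controlled exception through one study PI. General Guidance probably points to a stop for a clear myoglobin case, and the Renal Dysfunction rows add renal conditions at Grade 2 and above. Section 7.2.1 also describes these algorithms as suggested.

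Much of this stands. The sequential reading is possible and may be what was meant. But the row does not distinguish *signs* from *evidence*, and its resume sentence asks for cardiomyopathy, not kidney injury, to be excluded. The reader must supply the missing condition. The note adds an outcome rather than choosing between the existing two.

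Three stronger readings are tempting and are not supported:

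- *The row requires re-dosing.* It does not; the resume sentence is permissive.
- *The whole resume test is met at onset below Grade 4.* Only the CPK part is. The cardiomyopathy exclusion must still be met.
- *The ambiguity distorts arm-level discontinuation rates or the primary results.* The 3.6% is defined by multiples of baseline rather than CPK grade, comes from a different partner drug, and counts possible entrants to the row, not divergent decisions. About one expected patient cannot carry that claim. Section 9.1 analyses PFS in all randomized patients and ORR in all who initiated therapy, so neither definition depends on this row.

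**Conclusion.** The point holds as an internal contradiction in one table row. For a patient with CPK elevation of any grade, renal injury and no immune-related cardiomyopathy, both columns permit resumption and order permanent discontinuation, and nothing in the protocol says which governs. Below Grade 4 the CPK threshold also fails to discriminate, because it is met at entry.

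The contradiction is textual and rests on no numerical assumption. Its likely reach is small: about one Arm A patient if the proxy rate carries over, with a chance of at least one case of 69%, or 44% to 91% at half to twice that rate. That range is illustrative. The consequence is for patient safety and consistency between sites. No effect on the co-primary endpoint definitions is claimed, and no view is taken on which clinical rule is right.

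**What to change.** The sponsor should reconcile the row's entry criterion, resume sentence, permanent-stop sentence and starred note with one another, and with the CPK General Guidance row and the Renal Dysfunction rows. After the change, two situations should each lead to one unambiguous instruction in each column: Grade 4 CPK without organ injury, and CPK of any grade with cardiac or renal injury. The text should also make clear whether signs and evidence of injury are meant to differ, and what the starred note attaches to in Arm A. Which clinical rule applies in each situation is for the sponsor to decide.

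The cost is a wording change to one row and its cross-references in the next amendment. No patients, procedures or analyses are added.

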| Grade 2 hepatic event, $\leq 5$ days

*includes:
AST/ALT is $>\text{ULN}$ to $\leq 3 \times \text{ULN}$ at baseline and increases to $>5 \times \text{ULN}$ to $\leq 10 \times \text{ULN}$ | Continue atezolizumab & CDX-1127 (varlilumab).

Monitor LFTs biweekly until values resolve to baseline values.  | Continue atezolizumab & CDX-1127 (varlilumab) and cobimetinib.

Monitor LFTs biweekly until values resolve to baseline values.   |  |
| Grade 2 hepatic event, $>5$ days

*includes:
AST/ALT is $>\text{ULN}$ to $\leq 3 \times \text{ULN}$ at baseline and increases to $>5 \times \text{ULN}$ to $\leq 10 \times \text{ULN}$     | Hold atezolizumab & CDX-1127 (varlilumab).

Work to evaluate etiology of hepatic event. Consider patient referral to GI specialist for evaluation and liver biopsy to establish etiology of hepatic injury

If suspicion for immune-mediated process is high, initiate treatment with 1–2 mg/kg/day oral prednisone or equivalent.

If event resolves to grade 1 or better within 12 weeks, taper corticosteroids and resume atezolizumab according to the guidelines above.

Permanently discontinue atezolizumab & CDX-1127 (varlilumab) if event does not resolve to | Hold atezolizumab & CDX-1127 (varlilumab) and cobimetinib.

Work up to evaluate etiology of hepatic event. Consider patient referral to GI specialist for evaluation and liver biopsy to establish etiology of hepatic injury

If suspicion for immune-mediated process is high, initiate treatment with 1–2 mg/kg/day oral prednisone or equivalent.

If event resolves to grade 1 or better within 12 weeks, taper corticosteroids and resume atezolizumab & CDX-1127 (varlilumab) at fixed doses and cobimetinib at 1 dose reduction. |  |

|                            |  |  |
|----------------------------|--|--|

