## 9.5 Reporting and Exclusions

### 9.5.1 Evaluation of Toxicity

All patients will be evaluable for toxicity from the time of their first treatment with cobimetinib, atezolizumab, and CDX-1127 (varlilumab). A baseline measurement and at least 1 laboratory or other safety-related measurement obtained after at least 1 dose of study treatment may be required for inclusion in the analysis of a specific safety parameter (e.g., lab shifts from baseline). A complete list of all AE data will be provided along with an assessment of NCI CTCAE grade and relationship to study drug. The incidence of AEs will be tabulated by subgroups of interest (e.g. grade 3 or higher, organ class, relationship to study drug). For analyses at the individual level, the highest grade and relationship to study drug will be assumed if multiple events have occurred. Toxicity will be tabulated by type and grade and will be summarized with descriptive statistics. Other safety data will be assessed in terms of physical examination, clinical chemistry, hematology, vital signs, and ECGs. Negative binomial regression and Cox proportional hazards models will be used to assess the rate of AE and time to first toxicity, respectively.

While the combination of our proposed three study medications (or similar in-class alternatives) have not been studied in human trials, CDX-1127 (varlilumab) has been shown to be well tolerated in combination with anti-PD1, Nivolumab in patients with advanced solid tumors (NCT02335918). Additionally, the combination of cobimetinib and atezolizumab demonstrated a favorable safety profile at full doses in BTC patients (CTEP 10476). The present study will be continuously monitored for adverse events.

We will incorporate the following safety run-in and stopping rule that will be applied within each treatment group, A and B, respectively: if 2 or more “unacceptable toxicities,” at least possibly attributable to study therapy, are observed among the first 6 patients enrolled in the same treatment arm during their initial treatment cycle, we will pause the accrual in that arm and re-

evaluate safety. Accrual will be limited until the safety has been achieved in the first 6 patients in each arm, respectively.

“Unacceptable toxicities” are defined as the following treatment-related events:

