- Any grade  $\geq 2$  uveitis, retinitis, eye pain, or blurred vision that does not respond to topical therapy and does not improve to grade 1 severity within 2 weeks of starting therapy OR requires systemic treatment
- Recurrent grade 2 pneumonitis
- Symptomatic heart failure associated  $\geq 10\%$  reduction in LVEF
- Grade 3 uveitis, pneumonitis, bronchospasm, diarrhea, colitis, neurologic toxicity, hypersensitivity reaction, or infusion reaction
- Any grade 3 non-skin, drug-related AE lasting  $>7$  days, with the following exceptions:
  - Grade 3 endocrinopathies adequately controlled with only physiologic hormone replacement do not require discontinuation
  - Grade 3 laboratory abnormalities do not require treatment discontinuation except:
    - Grade 3 thrombocytopenia  $>7$  days OR that is associated with bleeding requires discontinuation
    - Any liver function test (LFT) abnormality that meets the following criteria require discontinuation:
      - Total bilirubin  $>3 \times$  ULN
      - Concurrent AST or ALT  $>3 \times$  ULN **and** total bilirubin  $>2 \times$  ULN
      - In participants with liver metastasis with baseline grade 2 elevation of AST or ALT, hepatitis with AST or ALT increases  $\geq 50\%$  and lasts  $\geq 1$  week
- Any grade 4 AE or laboratory abnormality, except for the following events which do not require discontinuation:
  - Grade 4 amylase or lipase abnormalities that are not associated with symptoms or clinical manifestations, or radiographic signs of pancreatitis. It is recommended to consult with the IND Sponsor for grade 4 amylase or lipase abnormalities.
  - Isolated grade 4 electrolyte imbalances/abnormalities that are not associated with clinical sequelae and are corrected with supplementation/appropriate management within 72 hours of their onset.
  - Grade 4 lymphopenia and leukopenia.
  - Grade 4 treatment-related endocrinopathy adverse events, such as adrenal insufficiency, ACTH deficiency, hyper- or hypothyroidism, or glucose intolerance, which resolve or are adequately controlled with physiologic hormone replacement (corticosteroids, thyroid hormones) or glucose-controlling agents, respectively, may not require discontinuation after discussion with and approval from the IND Sponsor.
- Any grade 5 adverse event
- Any dosing interruption lasting  $>6$  weeks with the following exceptions:
  - Dosing interruptions to allow for prolonged steroid tapers to manage drug-related adverse events are allowed.

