#### 10.3.4 Adverse Events of Special Interest

Adverse Event Special Interest (AESIs) are a subset of events of scientific and/or medical concern specific to this protocol, for which ongoing monitoring and communication by the Investigator to the Sponsor is required.

*General AESI:*

- Cases of potential drug-induced liver injury that include an elevated ALT or AST in combination with either an elevated bilirubin or clinical jaundice, as defined by Hy's Law and based on the following observations: - Treatment-emergent ALT or AST  $> 3 \times$  baseline value in combination with total bilirubin  $> 2 \times$  ULN (of which  $> 35\%$  is direct bilirubin) - Treatment-emergent ALT or AST  $> 3 \times$  baseline value in combination with clinical jaundice

Suspected transmission of an infectious agent by the study treatment, as defined below - Any organism, virus, or infectious particle (e.g., prion protein transmitting transmissible spongiform encephalopathy), pathogenic or non-pathogenic, is considered an infectious agent. A transmission of an infectious agent may be suspected from clinical symptoms or laboratory findings that indicate an infection in a patient exposed to a medicinal product. This term applies only when a contamination of study treatment is suspected.

*Atezolizumab:*

AESI for Atezolizumab are:

- Systemic lupus erythematosus
- Events suggestive of hypersensitivity, infusion-related reactions, cytokine-release syndrome, macrophage activating syndrome, hemophagocytic lymphohistiocytosis
- Nephritis
- Ocular toxicities (e.g., uveitis, retinitis, optic neuritis)
- Grade  $\geq 2$  cardiac disorders (e.g., atrial fibrillation, myocarditis, pericarditis)
- Vasculitis
- Autoimmune hemolytic anemia
- Severe cutaneous reactions (e.g., Stevens-Johnson syndrome, dermatitis bullous, toxic epidermal necrolysis)

*Cobimetinib:*

- AESI for Cobimetinib are:
- Any grade Serous retinopathy, including events of retinal detachment, retinal pigment epithelium detachment, neurosensory retinal detachment or central serous chorioretinopathy
- Significant liver toxicity: AST and/or ALT  $> 10 \times$  upper limit of normal
- Symptomatic heart failure / Grade  $\geq 2$  left ventricular dysfunction
- Grade  $\geq 3$  CPK elevation or Rhabdomyolysis
- Grade  $\geq 3$  Diarrhea
- Grade  $\geq 3$  rash

*Biopsy:*

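### Sections 7.3 and 9.5.1 give different dosing actions for a treatment-related Grade 2 rise in both transaminases and bilirubin, and neither says which prevails

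*Combined protocol and SAP*

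**What the plan says.** **Section 7.3, hepatotoxicity rows.** Hepatic events are sorted by grade and, within Grade 2, by duration. For Grade 2 up to 5 days the triplet column reads "Continue atezolizumab & CDX-1127 (varlilumab) and cobimetinib", and the doublet column continues both antibodies. The row's own note places in Grade 2 an AST/ALT above 5 and up to 10 x ULN when baseline was above ULN and up to 3 x ULN. For Grade 2 beyond 5 days the drugs are held, and may resume if the event settles to Grade 1 or better within 12 weeks. Grade 3 or 4 leads to permanent discontinuation of the antibodies, with cobimetinib held in the triplet column. No hepatic row sets a bilirubin cut-off or mentions a combined rise.

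**Section 9.5.1, unacceptable toxicities.** The list serves the safety run-in, covers treatment-related events, and contains the line "Any liver function test (LFT) abnormality that meets the following criteria require discontinuation". One criterion beneath it is "Concurrent AST or ALT $>3 \times$ ULN and total bilirubin $>2 \times$ ULN"; total bilirubin above 3 x ULN is a separate criterion. The line stands under the parent bullet "Grade 3 laboratory abnormalities do not require treatment discontinuation except", which itself stands under Grade 3 non-skin events lasting more than 7 days.

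**Section 10.3.4, adverse events of special interest.** This lists "Cases of potential drug-induced liver injury that include an elevated ALT or AST in combination with either an elevated bilirubin or clinical jaundice", with the transaminase limit set relative to baseline rather than ULN. It asks for monitoring and communication to the sponsor and sets no dosing action.

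**The concern.** A combined rise in transaminases and bilirubin is the pattern that Section 10.3.4 itself identifies with Hy's Law. On its natural wording, Section 9.5.1 takes the patient off treatment. The dose table, to which Section 6.1 sends sites for dose changes, continues treatment for up to 5 days and then holds it. Neither section refers to the other on this pattern.

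At stake is consistent handling of such a patient. Two sites with the same laboratory values could act differently, and a patient who counts as an unacceptable toxicity in the run-in could still be receiving study drug under Section 7.3.

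**Working it through.** No sample size, power or error rate is involved, so the check compares ranges.

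**Inputs**
- Section 9.5.1: AST or ALT above 3 x ULN and total bilirubin above 2 x ULN; no duration stated in that line.
- Section 7.3: Grade 2, up to 5 days, continue; Grade 2, more than 5 days, hold; Grade 3 or 4, antibodies discontinued.
- Section 3.1.5: AST/ALT up to 3 x ULN is allowed at entry, so the raised-baseline note in Section 7.3 applies to eligible patients.
- Assumption: the protocol names CTCAE v5.0 but does not print its limits. Grade 2 is taken as AST/ALT above 3 and up to 5 x ULN from a normal baseline, and bilirubin above 1.5 and up to 3 x ULN.

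**Two treatment-related examples, both on day 2**

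| AST/ALT baseline | AST/ALT now | Bilirubin now | 7.3 | 9.5.1 |
|---|---|---|---|---|
| normal | 4 x ULN | 2.5 x ULN | Grade 2, up to 5 days: continue | 4 > 3 and 2.5 > 2: criterion met |
| 2 x ULN | 8 x ULN | 2.5 x ULN | Grade 2 by the row's note (8 lies between 5 and 10): continue | 8 > 3 and 2.5 > 2: criterion met |

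If either event lasts beyond 5 days, Section 7.3 moves to a hold with possible resumption. That still differs from discontinuation.

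**Edges of the overlap**
- Transaminases: above 3 and up to 5 x ULN from a normal baseline, or above 5 and up to 10 x ULN from a raised one. Both ranges lie wholly above the 3 x ULN limit in Section 9.5.1.
- Bilirubin: above 2 and up to 3 x ULN. Above 3 x ULN the event is Grade 3 on the assumption, and Section 7.3 also stops the antibodies.

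**Sensitivity to the assumption.** If bilirubin above 2 x ULN were already Grade 3, every event meeting the combined criterion would fall in the Section 7.3 Grade 3 or 4 row and the overlap would be empty. The separate criterion at 3 x ULN in Section 9.5.1 fits a Grade 3 limit at 3 x ULN better, but the documents do not settle it.

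**Does the nesting confine the line to Grade 3?** It can be read so. Three features point the other way:
- The line covers any liver test abnormality that meets its criteria.
- It sets its own cut-offs. On the assumed grading a transaminase Grade 3 from a normal baseline is already above 5 x ULN, and a Grade 3 bilirubin already meets the separate criterion. The 3 x ULN transaminase limit would then have nothing left to do.
- Other items in the same list state durations where they want one (thrombocytopenia beyond 7 days, hepatitis for at least 1 week). This one states none.

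**The case against.** The strongest case against is that the two texts do different jobs. Section 9.5.1 defines what counts in a run-in of the first 6 patients per arm during their first cycle, and the consequence of 2 or more events is a pause in that arm's accrual. Dose changes belong to Section 7. Read with its parent bullets, the liver line concerns Grade 3 laboratory events, for which Section 7.3 already discontinues the antibodies. This stands to the extent that the scope of the line is ambiguous. It does not remove the problem, because the line speaks of discontinuing treatment and not only of counting events.

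The existing safeguards also deserve weight. Section 7.2.2 has all three agents held or discontinued in Arm A when the responsible drug is unclear, and asks for liver and biliary imaging when liver tests rise. Section 7.1.1 asks for a benefit-risk assessment before further antibody dosing. None of these gives a rule for the combined pattern.

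Several stronger conclusions might be inferred, and the documents do not support them:
- *Every Hy's Law case is in conflict.* Only the Grade 2 part is.
- *Laboratory values alone trigger Section 9.5.1.* It requires a treatment-related event, whereas the Section 7.3 rows also ask about a tumour-related cause. In biliary cancer some combined rises will fall outside Section 9.5.1.
- *The run-in count depends on which section a site reads.* The count is fixed by Section 9.5.1, whatever dosing Section 7.3 directs.
- *Section 10.3.4 is a third dosing rule.* It prescribes no dosing action.
- *Such events will often be found just before an infusion.* Chemistry may be drawn up to 3 days before dosing, but infusions are 14 days apart and the row that continues treatment covers at most 5 days. No frequency can be derived from that.

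**Conclusion.** The point holds in limited form. For a treatment-related combined rise that is still Grade 2, Section 7.3 continues and then holds treatment, while the natural wording of Section 9.5.1 discontinues it, and nothing says which prevails. The conclusion rests on two things: a CTCAE v5.0 bilirubin Grade 3 limit of 3 x ULN, and reading the 9.5.1 line as not confined to Grade 3. If either fails, this Grade 2 conflict goes, though the 9.5.1 line would still need clarifying.

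Few patients are expected, and the documents contain no applicable rate. The one figure for a similar pattern, 0.4% in Section 2.2.2.2.3, comes from cobimetinib plus vemurafenib in melanoma and also requires the absence of a significant alkaline phosphatase rise. Taken at face value it would give 0.004 x 64 = 0.26 patients, but it should not be carried over to this regimen and disease.

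The run-in rule and its count are unaffected. The consequence is inconsistent dosing of a patient who may count as an unacceptable toxicity. Because this concerns stopping drug for a liver-injury signal and is cheap to resolve, it merits correction despite its narrow scope.

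**What to change.** Reconcile the hepatic rows of Section 7.3 with the liver criteria of Section 9.5.1:
- State in the Section 7.3 hepatic rows how a concurrent AST/ALT and bilirubin rise is handled.
- Use the same cut-offs and the same action in Section 9.5.1, and say whether that line is limited to Grade 3 events.
- Cross-refer both to Section 10.3.4, and note that its transaminase limit is relative to baseline.

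Which action is right is for the clinical team. The cost is a few lines of text at the next amendment. No tests are added, because AST, ALT and bilirubin are already in the chemistry panel of the study calendar.
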